7.0 STATISTICAL ANALYSIS PLAN

The primary objective of this phase II trial is to assess the efficacy of MK-3475 as a single agent in metastatic IBC and non-IBC TNBC patients. The primary endpoint is the rate of disease control measured at the end of 4 months from the start of therapy.

The disease control rate is defined as the percentage of patients either 1) with measurable disease that achieve iCR, iPR, iSD, or 2) with non-measurable disease that achieve iCR or iSD, , by 4 months or more in all evaluable patients. We will also perform secondary analysis on intent-to-treat patient population where those patients who drop out early will be considered as progression.

The trial will be conducted using Simon's optimal two-stage design and the rate of disease control will be estimated accordingly. It is assumed that the MK-3475 single agent will have a disease control rate of 30%. A disease control rate of 10% or lower will be considered treatment failure and the regimen will be rejected under this circumstance. When the probability of accepting a "bad" regimen (i.e. disease control rate 10% or lower) is 0.10 and the probability of rejecting a "good" regimen (i.e. disease control rate 30% or higher) is also 0.10, Simon's optimal 2-stage design requires 12 patients enter in the first stage. The study accrual will be delayed until all 12 patients are evaluable for disease control status. If 1 or no patients maintain disease control on treatment, the trial will be stopped and the regimen will be declared as ineffective. If 2 or more patients maintain disease control, 23 more patients will be enrolled to the study to reach a total of 35 treated patients. By the end of the study, the new regimen will be rejected if rate of disease control is less than or equal to 5/35 and will be considered worthy of further investigation otherwise.

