However, with a larger sample size, we will be able to detect a smaller target disease control rate of 0.25. It is assumed that the MK-3475 single agent will have a disease control rate of 25%. A disease control rate of 10% or lower will be considered treatment failure and the regimen will be rejected under this circumstance. When the probability of accepting a "bad" regimen (i.e. disease control rate 10% or lower) is 0.10 and the probability of rejecting a "good" regimen (i.e. disease control rate 25% or higher) is also 0.10, Simon's optimal 2-stage design requires 21 patients enter in the first stage. The study accrual will be delayed until all 21 patients are evaluable for disease control status. If 2 or less patients maintain disease control on treatment, the trial will be stopped

and the regimen will be declared as ineffective. If 3 or more patients maintain disease control, 29 more patients will be enrolled to the study to reach a total of 50 treated patients. By the end of the study, the new regimen will be rejected if rate of disease control is less than or equal to 7/50 and will be considered worthy of further investigation otherwise. But, that will not happen based on the current disease control rate.

At any time after first 5 patients are treated, if $\geq 30\%$ patients experience serious adverse events (SAE) within 2 cycles of treatment, we will stop the trial and claim that the regimen is too toxic. SAE is defined as an adverse event is serious, unexpected, and related to the study drug.

Patients' characteristics will be summarized at the end of the study. For discrete or categorical data, descriptive statistics will be generated including tabulations of frequencies. For continuous data, summary statistics including sample size, mean, standard deviation, median, minimum and maximum will be computed. A 95% exact binomial confidence interval on disease control rate will be computed.

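### Section 7.0 keeps two complete Simon designs (12/35 and 21/50) and was written with trial results known, so 0.10/0.10 is not established for the 50-patient decision

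*Combined protocol and SAP*

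**What the plan says.** All of this is in Section 7.0 of the combined protocol and SAP.

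- **First design.** The null rate is 10% ("A disease control rate of 10% or lower will be considered treatment failure") and the target is 30%. For the first stage, "Simon's optimal 2-stage design requires 12 patients enter in the first stage"; then "If 1 or no patients maintain disease control on treatment, the trial will be stopped". Otherwise "23 more patients will be enrolled to the study to reach a total of 35 treated patients". At the end, "the new regimen will be rejected if rate of disease control is less than or equal to 5/35".
- **Second design.** It is introduced by "However, with a larger sample size, we will be able to detect a smaller target disease control rate of 0.25". The null rate stays at 10% and the target becomes 25%. The first look is at 21 patients, stopping at 2 or fewer controlled. Another 29 patients bring the total to 50, with rejection at 7/50 or fewer.
- **Error rates.** Both designs are stated with 0.10 for accepting a bad regimen and 0.10 for rejecting a good one.
- **Forecast.** Directly after the second final rule comes "But, that will not happen based on the current disease control rate".

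The trial summary (Section 1.0) lists 50 subjects and an open-label design. Section 4.6 makes the principal investigator responsible for monitoring disease control. The plan does not give the current rate, its denominator, the date of the change, or which first-stage look was applied.

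**The concern.** A two-stage design has its stated error rates only when the sample sizes, cut-offs and target are set without knowledge of the outcomes and the trial then follows those stages. Section 7.0 leaves both conditions open. A current disease control rate can only come from patients treated in this trial, so whoever wrote that sentence knew primary-endpoint results. The second design also follows the first as an add-on, so the first may already have been in operation, including its 12-patient look.

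At stake is the error statement attached to the final conclusion. The trial could be reported as a 10% false-positive, 90% power test at 25% when the path followed had other properties. The two sets of rules can also return different answers on the same data, and the plan does not say which one prevails.

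**Working it through.** **Inputs (Section 7.0).** p0 = 0.10. First design: r1/n1 = 1/12, r/n = 5/35, p1 = 0.30. Second design: r1/n1 = 2/21, r/n = 7/50, p1 = 0.25.

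**Step 1: reproduce the plan's figures.** The probability of declaring the regimen worthy at true rate p is

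A(p) = Σ (x = r1+1 to n1) b(x; n1, p) · P(Y ≥ r + 1 − x), with Y ~ Bin(n − n1, p).

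| Design | A(0.10) | A(p1) | Early stop at 10% | Expected N at 10% |
|---|---|---|---|---|
| 1/12, 5/35 | 0.0977 | 0.9014 (30%) | 0.659 | 12 + 0.341 × 23 = 19.8 |
| 2/21, 7/50 | 0.0979 | 0.9008 (25%) | 0.648 | 21 + 0.352 × 29 = 31.2 |

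A full search for the smallest expected N under 10%, with type I error at most 0.10 and power at least 0.90, returns these same two designs. The arithmetic in the plan is correct.

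**Step 2: effect of the 12-patient look on a 25% drug.** P(X ≤ 1 | 12, 0.25) = 0.75^12 + 12 × 0.25 × 0.75^11 = 0.0317 + 0.1267 = 0.158. On any path that used this look, power at 25% cannot exceed 1 − 0.158 = 0.842.

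**Step 3: paths from 12 to 50.** The documents do not describe the path, so these are assumptions. All include the 12-patient look (continue with at least 2 controlled).

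| Assumed path | Type I error (10%) | Power at 25% |
|---|---|---|
| Look at 12, then on to 50, success at 8 or more | 0.083 | 0.820 |
| Looks at 12 and 21, then 8/50 | 0.077 | 0.807 |
| Success at 6/35 or more; otherwise extend, success at 8/50 | 0.118 | 0.827 |
| Extend only with at least 6/35, then require 8/50 | 0.063 | 0.788 |

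Type I error falls below 0.098 on three paths and rises on one. Power at 25% is below 0.90 on all four.

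**Step 4: conditional on data in hand.** If the 50-patient rule was adopted after m patients with s controlled, the chance of reaching 8/50 is P(Bin(50 − m, p) ≥ 8 − s). For a drug with a true rate of 10%:

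| Controlled/treated at the change | 3/12 | 5/21 | 6/35 | 7/35 | 8 or more |
|---|---|---|---|---|---|
| Chance of 8/50 | 0.33 | 0.57 | 0.45 | 0.79 | 1.00 |

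This is why the counts at the date of the change matter.

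**Step 5: conflicts between the rules.**
- 6/35 then 7/50: the first design says worthy (6 > 5); the second rejects (7 ≤ 7).
- 1/12 then 3/21: the first design stops; the second continues.
- 2/12 then 2/21: the first design continues; the second stops.

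**The case against.** **Timing.** The forecast shows what was known when that sentence was written, not when 50 patients and 25% were chosen. The stated reason for the second design is that a larger sample detects a smaller effect; no observed rate is cited. If the 21/50 rule was fixed before any outcome was seen, the sentence was added later and the 12-patient look was not used, 0.098 and 0.901 stand. This objection holds. Knowledge at the redesign is a reasonable inference, not a documented fact.

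**Inflated false-positive rate.** A reader might take 0.118 as the real type I error. The documents do not support that. No section describes the path. Its excess over the 35-patient design (0.1177 − 0.0977 = 0.020) comes only from trials with 5 or fewer controlled at 35 that are extended and rescued. From 5/35, the chance of ending at 7/50 or fewer is 0.82 at a true rate of 10% and 0.24 at 25%, which does not fit the confidence of the forecast. If 8 or more were already controlled within the first 35, the 6/35 criterion was met as well, so the redesign did not create that verdict.

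**A rule that cannot fail.** A reader might infer that the final test was declared settled. That would be literally so only if at least 8 patients already had disease control, and no count is given. The sentence is a loose forecast, its referent is not certain, and the 7/50 rule stays in the text.

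**Power.** The 12-patient look was designed for 30%, where it stops a good drug with probability 0.085, and the path from 12 straight to 50 has power 0.911 at 30%. That is fair. But the plan's 90% claim for the second design is made at 25%, so 25% is the rate at which to judge it.

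**Conclusion.** The concern holds in a limited form. Section 7.0 contains two full designs with different looks and cut-offs, does not say which governs, and was written when primary-endpoint results were known. Neither design is miscalculated.

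The stated 0.10/0.10 describes the 50-patient decision only if the 21/50 rule was fixed before outcomes were seen and the 12-patient look was not used. The plan establishes neither. If the 12-patient look applied, power at 25% is about 0.79 to 0.83 on the paths computed, against the stated 0.90. The direction of any change in type I error is not determined.

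The documents do not prove that the redesign was driven by results, that the type I error exceeds 0.10, or that the final rule could not fail. Section 1.0 lists 50 subjects, which suggests that the second design governs. That does not settle when it was fixed or which first look was used. The point should be corrected before the decision is reported. Confidence is medium because the sequence of events is not dated.

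**What to change.** 1. Delete the forecast sentence.
2. State the date on which the size, target and cut-off changed, and the numbers treated, evaluable and controlled on that date.
3. Name one governing decision rule and one first-stage look, and mark the other design as superseded.
4. If outcomes were known at the change, choose one of two routes:
   - Report the 12/35 verdict (at least 6/35) on the first 35 patients as the pre-specified decision, and treat later patients as an expansion for estimation. If its 12-patient look was followed, this design has type I error 0.098 and power 0.901 at 30%; its power at 25% is 0.795.
   - Keep 8/50 as the criterion, but replace 0.10/0.10 with exact error rates for the path actually followed, conditional on the data in hand at the change.
5. If outcomes were not known at the change and the 12-patient look was not used, say so; 0.098 and 0.901 at 25% then apply.

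Neither 0.82 nor 0.118 should be written into the plan as a fixed value, because each depends on an assumed path.

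The cost is SAP wording and a short exact calculation, with no extra patients. The downside is a less favourable error statement.

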Various biomarker endpoints will be measured in various specimens. Correlation among biomarkers at baseline in each specimen and between different specimens will be assessed. The association among various continuous and discrete biomarkers or disease status groups will be assessed by the exploratory data analysis using scatter plot matrix, box plots, BLIP plot³⁷ and trellis plot, etc, and may be tested by t-test/ANOVA/Wilcoxon rank sum test/Kruskal-Wallis test, whichever is appropriate. Correlation between continuous biomarkers will be examined by Pearson or Spearman rank correlation coefficients. The association between discrete biomarkers will be tested by chi-square or Fisher's exact test. Paired t-test/Wilcoxon rank sum test and McNemar's test may be used to test the change of a single continuous biomarker and discrete biomarker, respectively, over time within each treatment group. Repeated measures analysis including mixed effects model will be performed to analyze the correlation between disease control and biomarkers change over time.³⁸ Disease control survival and overall survival time from the registration date will be estimated using Kaplan-Meier method.

All statistical tests will be performed at a two-sided significance level of 5% using SAS or S-Plus, as appropriate.

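### The planned 95% exact binomial interval for the disease control rate ignores the two-stage design, and its level does not match the one-sided 0.10 decision rule

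*Combined protocol and SAP*

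**What the plan says.** All of this is in the combined protocol and SAP, section 7.0 Statistical Analysis Plan.

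- Design and estimation: "The trial will be conducted using Simon's optimal two-stage design and the rate of disease control will be estimated accordingly". No estimator is named.
- Two designs are set out, both with a failure rate of 10% and both error probabilities at 0.10. With a 30% target, 12 patients enter stage one, and "If 1 or no patients maintain disease control on treatment, the trial will be stopped and the regimen will be declared as ineffective"; otherwise the trial goes to 35 and the regimen is rejected at 5/35 or fewer. With a 25% target, stage one has 21 patients, the trial stops at 2 or fewer, and otherwise goes to 50, where "the new regimen will be rejected if rate of disease control is less than or equal to 7/50". The regimen therefore passes from 6/35 or from 8/50.
- Interval: "A 95% exact binomial confidence interval on disease control rate will be computed". No adjustment for the two stages is mentioned.
- Test level, at the end of the section: "All statistical tests will be performed at a two-sided significance level of 5" per cent.

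Nothing says how the interval relates to the decision rule.

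**The concern.** Two separate mismatches are involved.

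The first is the sample space. A fixed-sample exact interval treats 8/50 as one draw of 50 patients. In this trial a total of 8/50 can arise only if at least 3 of the first 21 had disease control, and poor results at stage one end the trial. Tail probabilities that leave out the stopped trials are wrong, and so are limits derived from them.

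The second is the level. The rule accepts a 0.10 one-sided error against 10%, whereas a two-sided 95% interval allows 0.025 per tail. A report could call the regimen worthy of further investigation beside an interval that includes the plan's own failure rate, with nothing in the plan to explain why. What is at stake is the reporting and reading of the primary result.

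**Working it through.** **Inputs (section 7.0).** p0 = 0.10. Design A: r1/n1 = 1/12, r/n = 5/35, target 0.30. Design B: r1/n1 = 2/21, r/n = 7/50, target 0.25. The trial summary gives 50 subjects, but section 7.0 describes both designs, so both were computed.

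**Model.** X1 ~ Bin(n1, p) and X2 ~ Bin(n − n1, p). If X1 ≤ r1 the trial stops; otherwise S = X1 + X2.

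**Step 1: reproduce the plan's designs.** P(pass) = P(X1 > r1, S > r).
- Design A: 0.0977 at 10% and 0.9014 at 30%; chance of early stopping at 10% is 0.659.
- Design B: 0.0979 at 10% and 0.9008 at 25%; chance of early stopping at 10% is 0.648.

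A full search for Simon's optimal design returns exactly these two. The decision rule is sound as stated.

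**Step 2: the two intervals at and just above the boundary.** The ordinary interval is Clopper-Pearson on s/n. The two-stage interval (stagewise ordering) solves, with a = 0.025 for 95% or 0.10 for 80%:
- lower limit: P(X1 > r1, S ≥ s) = a
- upper limit: P(X1 ≤ r1) + P(X1 > r1, S ≤ s) = a

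If the trial stops at stage one, these reduce to the ordinary interval on n1, so differences arise only after stage two.

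| Total | x/n | Ordinary 95% | Two-stage 95% | Ordinary 80% | Two-stage 80% |
|---|---|---|---|---|---|
| 8/50 | 16.0% | 7.2–29.1 | 7.5–31.7 | 9.5–24.7 | 10.05–26.3 |
| 9/50 | 18.0% | 8.6–31.4 | 8.8–33.0 | 11.2–26.9 | 11.5–27.9 |
| 10/50 | 20.0% | 10.03–33.7 | 10.2–34.6 | 12.8–29.1 | 13.0–29.7 |
| 6/35 | 17.1% | 6.6–33.6 | 7.1–39.2 | 9.3–28.2 | 10.06–31.3 |
| 7/35 | 20.0% | 8.4–36.9 | 8.8–40.4 | 11.5–31.3 | 12.1–33.3 |
| 8/35 | 22.9% | 10.4–40.1 | 10.7–42.2 | 13.8–34.5 | 14.2–35.6 |

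At the ordinary upper limit for 8/50 (p = 0.2911), the tail that should be 0.025 is P(X1 ≤ 2) + P(X1 > 2, S ≤ 8) = 0.0328 + 0.0168 = 0.0496. For 6/35 (p = 0.3365) it is 0.0516 + 0.0157 = 0.0672.

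**Step 3: coverage of the ordinary 95% interval over all outcomes.** Coverage is 1 minus the probability of outcomes whose interval misses p.
- Design B, p just above 31.44% (the ordinary upper limit for 9/50). Stage-one stops have upper limits of 16.1%, 23.8% and 30.4%, so all miss: 0.0198. Totals up to 9/50 miss: 0.0191. Upper-tail error is 0.0198 + 0.0191 = 0.0389, against a nominal 0.025. Totals of 23/50 or more miss from above: 0.0217. Coverage = 1 − 0.0389 − 0.0217 = 0.939.
- Design A, p just above 38.48% (the upper limit for 1/12). Stage-one stops 0.0250, totals up to 7/35 0.0118, totals of 20/35 or more 0.0194. Coverage = 1 − 0.0368 − 0.0194 = 0.944.

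At round true rates between 5% and 50%, coverage stays at 95.7% or more; the dips lie between those rates.

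**Step 4: how often the level mismatch would show.** The chance of finishing at 8 or 9 of 50 is 21%, 20% and 9% at true rates of 15%, 20% and 25%. The chance of finishing at 6 or 7 of 35 is 21%, 24% and 8% at 15%, 20% and 30%.

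**Step 5: the point estimate, if x/n is used.** Averaged over all outcomes, x/n is biased low: −1.5, −1.7, −1.3 and −0.7 points at 10%, 15%, 20% and 25% (design B); −2.3, −2.7, −2.5 and −1.3 points at 10%, 15%, 20% and 30% (design A). Among trials that reach stage two it is biased high: +3.1 points at 10% and +0.6 at 25% (design B); +3.5 at 10% and +0.7 at 30% (design A). The uniformly minimum-variance unbiased estimate (UMVUE) is 18.7% at 8/50 and 21.9% at 6/35.

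**The case against.** The strongest reply is that the interval is only descriptive. It stands in the paragraph on summary statistics, the decision is made by counts, no p-value for the primary endpoint is planned, and the ordinary interval covers at least 95% at most true rates. The two-sided 5% sentence follows the biomarker analyses, and the primary rule has its own stated error rates. Most of this stands and keeps the point minor. It does not make the interval exact under the design, and the plan nowhere says that the interval is descriptive or that the 5% sentence excludes the primary endpoint.

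Three stronger readings are tempting and are not supported.

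- A reader might infer that ignoring the stopping rule is what makes the 95% interval contradict the decision. The table shows otherwise: the two-stage 95% interval also includes 10% at 8–9/50 and 6–7/35, and both versions first exclude it at 10/50 and 8/35. That conflict comes from the level. The stopping rule alone decides only at 8/50 and 6/35, once the level is matched at 80%.
- A reader might infer that the reported rate will understate the effect when the trial continues. Given continuation, x/n is biased high; the low bias appears only on averaging over stopped trials. Nor does the plan commit to x/n: it says that "the rate of disease control will be estimated accordingly" and names no estimator. Preferring the UMVUE is a choice, since among continuing trials it overestimates by more (+7.3 points at 10% and +1.4 at 25% in design B).
- A reader might infer that the go/no-go decision is compromised. Its error rates reproduce.

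**Conclusion.** The concern holds in a limited form. The interval is a fixed-sample one applied to a two-stage trial. Near the boundary its upper limit is too low by 2.6 points at 8/50 (31.7 − 29.1) and 5.6 points at 6/35 (39.2 − 33.6). Coverage falls to about 94%, and upper-tail error reaches about 3.9% against a nominal 2.5%. Separately, the 95% level does not match the one-sided 0.10 rule, so a passing result of 8–9/50 or 6–7/35 will be reported beside an interval that includes 10% whichever 95% method is used.

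Severity is minor: reporting is affected, the decision rule is not. The figures assume that the stage sizes and boundaries are followed exactly, that one of the two stated designs governs, and that the two-stage interval uses stagewise ordering. Another ordering would shift the limits somewhat.

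**What to change.** Replace the interval sentence in section 7.0 with wording such as: *Confidence intervals for the disease control rate will be exact intervals computed on the two-stage sample space (stagewise ordering). A two-sided 80% interval, which matches the one-sided 0.10 decision rule, will be reported together with a two-sided 95% interval. The 95% interval is descriptive and is not used for the decision.*

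Also:
- limit the two-sided 5% sentence to the exploratory tests;
- name the point estimator, which the plan leaves open. Reporting x/n with the UMVUE beside it is a reasonable option, though not a necessary one.

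The cost is a few sentences and a few lines of code. Upper limits near the boundary become somewhat higher. No patients, data or changes to the decision rule are needed.

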6.2.2 Blood samples

Collection and processing

Multiple blood draws will be required for this trial. All blood tubes will be labeled only with the patients' unique study number. Approximately 100cc will be drawn for each immunologic assessment (at baseline; prior to dosing of study drug with every third cycle i.e. cycle 3, 6, 9, 12 etc , or every other cycle after for patients who start Pembrolizumab 400mg at C9 and beyond; and at disease progression). 10cc will be collected into a BD Vacutainer Rapid Serum tube (BD, Franklin Lakes, NJ) which contains a clot activator and silicone coated interior. After

centrifugation, serum will be collected, aliquoted in 1cc vials and frozen. 70cc will be collected into BD Vacutainer CPT Cell Preparation tubes which contain an anticoagulant (sodium heparin or sodium citrate) with FICOLL HYPAQUE density gradient fluid and a polyester gel barrier. The density gradient fluid and the gel barrier allow for the separation of peripheral blood mononuclear cells (PBMC) from the red blood cells by a single step centrifugation process. The PBMC fraction will be collected by centrifugation and suspended in RPMI-1640 (GIBCO, Invitrogen Corporation, Carlsbad, CA) with 10% FCS (Gemini Bio-Products, West Sacramento, CA) and antibiotics. Plasma will be collected from CPT Cell Preparation tubes and stored. 20cc blood will be collected in heparin 10ml green top tubes for FACS assay.

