6.2.3 Assays

Serum

- Soluble factors such as cytokines and chemokines present in serum collected at baseline, during, and after treatment will be quantified using a multiplex assay which has the capability to simultaneously measure multiple analytes from a single sample. Factors to be evaluated may include but not necessarily be limited to IFN- γ , TNF- α , IL-2, IL-4, IL-5, IL-7, IL-10, IL-12, IL-15 and IL-17.
- Additional immunoassays will be performed to quantify soluble receptors present in the serum. Analyses may include but not necessarily be limited to soluble CD25, soluble PD-1, and soluble LAG-3.

Peripheral blood mononuclear cells

- The proportion of specific lymphocyte subsets to include T cells, B cells, and the proportion of memory and effector T cell subsets will be quantified by flow cytometry.
- The expression levels of T cell co-stimulatory and co-inhibitory markers including but not necessarily limited to PD-1, PD-L1, other B7 family members, and ICOS will be quantified by flow cytometry.

Plasma

- Exosomal RNA-sequencing will be performed with RNA extracted from plasma by Insight Genetics, Inc along with the tumor sample listed in section 6.2.1. There is only one time point plasma sample needed, and plasma samples at baseline will be preferred, but samples collected at other time points can be substitute if the baseline sample is unavailable.
- Plasma will be stored for future research purpose.

FACS assay

- Intracellular cytokine synthesis by T-cells activated through the T-cell receptor (TCR).
- Cytokine production by dendritic cells activated with Toll-like receptor (TLR) agonist.

- The NK cell assay.

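### For within-patient biomarker change the plan names the Wilcoxon rank sum test, an independent-samples test; it should name the signed-rank test (minor wording error)

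*Combined protocol and SAP*

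**What the plan says.** The biomarker paragraph of section 7.0 has two sentences that bear on this.

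- **Comparisons between groups.** Associations of markers with each other or with disease-status groups "may be tested by t-test/ANOVA/Wilcoxon rank sum test/Kruskal-Wallis test, whichever is appropriate".
- **Change over time.** For one continuous marker the plan lists "Paired t-test/Wilcoxon rank sum test" as options, and for a discrete marker McNemar's test. The change in question is the one seen "over time within each treatment group".

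The closing line of section 7.0 sets a two-sided 5% level for all tests. Section 1.0 lists a single treatment group. Under section 6.2.2, blood is taken at baseline, "prior to dosing of study drug with every third cycle i.e. cycle 3, 6, 9, 12 etc" (every other cycle for patients on the six-weekly schedule from cycle 9), and at progression. Section 6.2.3 adds that soluble factors such as "cytokines and chemokines present in serum collected at baseline, during, and after treatment will be quantified".

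**The concern.** In a one-group trial with serial samples, a test of change in one marker compares two values from the same patient. The paired t-test and McNemar's test respect that pairing. The rank sum test does not: it treats the baseline values and the on-treatment values as two unrelated groups of people.

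An analyst who follows the sentence literally would discard the pairing. If a patient's two values are positively correlated, as is usual for repeated measurements, the test rejects too seldom and a real change can be missed. It would not produce extra false positives. The markers affected are those measured more than once, such as serum cytokines. The exosome RNA work (exploratory objective 3) needs only one plasma time point and is not affected.

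**Working it through.** **The wording.** The tests named in section 7.0 can be set side by side:

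| Purpose | Parametric | Rank-based | Discrete |
|---|---|---|---|
| Between groups | t-test, ANOVA | rank sum, Kruskal-Wallis | chi-square, Fisher |
| Within patient, over time | paired t-test | rank sum | McNemar |

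The first row is consistent. In the second row every entry is a paired test except the rank-based one. The same test name therefore stands for two different comparisons, and signed-rank appears nowhere in the documents.

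**Size of the effect.** The plan gives no sample size, power or effect size for this analysis, so there is no figure to reproduce. The following is illustration only.

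*Inputs.* Two-sided 5% level (section 7.0). 35 pairs, the total of the first two-stage design in section 7.0; 50, the total of the second, and 20 are also tried. Assumed: within-patient correlation ρ from 0 to 0.7 and a shift of 0.5 SD. Data are normal, or lognormal with log-SD 1, the shift on the log scale and raw differences analysed.

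*Level, by formula.* Under no change, pairing multiplies the large-sample variance of the rank sum statistic by 1 − ρ_S. Here ρ_S is the Spearman correlation, which for bivariate normal data is (6/π)·arcsin(ρ/2). The true level is then about 2·{1 − Φ(1.96/√(1 − ρ_S))}.

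- ρ = 0.2: ρ_S = 0.191, 1.96/0.899 = 2.18, level 0.029
- ρ = 0.3: ρ_S = 0.288, 1.96/0.844 = 2.32, level 0.020
- ρ = 0.5: ρ_S = 0.483, 1.96/0.719 = 2.72, level 0.006
- ρ = 0.7: ρ_S = 0.683, 1.96/0.563 = 3.48, level 0.0005

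*Level and power, by simulation* (10,000 data sets per setting, normal-approximation p-values, 35 pairs):

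| ρ | Rank sum, true level | Rank sum, power | Signed-rank, normal | Signed-rank, lognormal |
|---|---|---|---|---|
| 0 | 0.05 | 0.52 | 0.51 | 0.47 |
| 0.2 | 0.03 | 0.52 | 0.60 | 0.54 |
| 0.3 | 0.02 | 0.52 to 0.53 | 0.65 | 0.59 |
| 0.5 | 0.008 | 0.52 | 0.80 | 0.73 |
| 0.7 | 0.001 | 0.54 | 0.95 | 0.91 |

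The rank sum result does not depend on whether the data are logged, so one power column serves both distributions. Signed-rank keeps its level near 0.05. The simulated levels agree with the formula.

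*Power lost by using rank sum (signed-rank minus rank sum):*

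- ρ = 0: none. Rank sum is ahead by 0.52 − 0.51 = 0.01 (normal) or 0.52 − 0.47 = 0.05 (lognormal).
- ρ = 0.2: 0.60 − 0.52 = 0.08 (normal); 0.54 − 0.52 = 0.02 (lognormal).
- ρ = 0.3: 0.65 − 0.53 = 0.12; 0.59 − 0.52 = 0.07.
- ρ = 0.5: 0.80 − 0.52 = 0.28; 0.73 − 0.52 = 0.21.
- ρ = 0.7: 0.95 − 0.54 = 0.41; 0.91 − 0.54 = 0.37.

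*Sensitivity at ρ = 0.5, signed-rank against rank sum.* The first on-treatment draw is at cycle 3, so some treated patients may contribute no pair.

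- 20 pairs: 0.54 against 0.26 (normal), 0.48 against 0.27 (lognormal).
- 50 pairs: 0.92 against 0.74 (normal), 0.88 against 0.74 (lognormal).
- 35 pairs with a smaller shift of 0.4 SD: 0.61 against 0.33 (normal).

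*The paired t-test already offered.* At ρ = 0.5 with 35 pairs its power is 0.82 on normal data and 0.56 on raw lognormal data.

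**The case against.** The best defence is that the intention is plain. The sentence opens with the word paired, places McNemar's test alongside and speaks of change within a group. One can read *paired* as covering both continuous-data tests, in which case a competent analyst would run a paired Wilcoxon test anyway. That reading is reasonable and is why this counts as a slip of name. It does not make the name right, because the same paragraph uses rank sum in its proper sense for group comparisons.

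The remaining objections concern weight, and most of them stand:

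- **No objective depends on this test.** Exploratory objectives 1 and 3 ask about association with safety or efficacy; 2 and 4 are the disease control rate and 5-year survival.
- **The test is optional, and a valid paired t-test stands beside it.** Skewed markers could be transformed first, which would answer the weak t-test result on raw lognormal data. The plan does not mention transformation.
- **The error is conservative** under positive correlation, and the sizes above rest wholly on assumed inputs.

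Two other defences do not help. The latitude to use whichever test is appropriate belongs to the group-comparison sentence. The mixed model does allow for repeated measures, but its stated purpose is to relate disease control to biomarker change, not to test change in a single marker.

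**Conclusion.** The point holds as a minor wording error. The named test does not fit the paired comparison described, and the plan names no correct rank-based alternative. If the sentence were followed literally with 35 pairs and a 0.5 SD shift, the power lost would range from nothing at correlation 0, through 2 to 12 points at 0.2 to 0.3, to 21 to 41 points at 0.5 to 0.7. The true level would lie below 5% at every positive correlation examined. These figures depend on the assumed correlation, shift, number of pairs and distribution. The conclusion about the test's name does not. The primary endpoint, two-stage decision rule, toxicity rule and sample size are untouched.

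**What to change.** In the sentence of section 7.0 on change over time, replace *Wilcoxon rank sum test* with *Wilcoxon signed-rank test*. Keep rank sum in the earlier sentence on group comparisons, where it is correct.

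This is a one-phrase edit that needs no new data, samples or patients. The only statistical cost arises if within-patient correlation is close to zero, where signed-rank is slightly less powerful (0.51 against 0.52 on normal data and 0.47 against 0.52 on lognormal data, with 35 pairs).
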